[REDACTED] In the short-term studies (8 weeks duration and less) for the development of Glanatec, there were no [REDACTED] [REDACTED] (Kowa Company Ltd 2019).

Kowa proposes to pursue development of K-321 (ripasudil ophthalmic solution) for the following indication: “the treatment of Fuchs corneal dystrophy after descemetorhexis.” This will be the first Kowa-sponsored study in patients for this indication.

Objectives:

Primary Objective:

The primary objective of this study is to investigate the effect of K-321 dosed for 12 weeks on central ECD in patients with FECD after descemetorhexis.

Secondary Objectives:

The secondary objectives of this study are the following:

- to investigate the effect of K-321 on central ECD, corneal thickness, and corneal clarity in patients with FECD at each visit after descemetorhexis out to 52 weeks
- to assess the safety and tolerability of K-321 in patients with FECD at each visit after descemetorhexis out to 52 weeks

Exploratory Objectives:

[REDACTED]

Study Design:

This is a multi-centre, double-masked, randomised, parallel-group, placebo-controlled, 2-period study of patients with FECD after descemetorhexis.

The first period is the treatment period, consisting of a screening visit within a 1- to 4-week screening period, a descemetorhexis and randomisation visit, a 12-week full treatment period containing 7 interim visits (including 1 optional visit at Week 2) and an end-of-treatment (EOT) visit scheduled for Week 12. During the 2 weeks immediately following the EOT visit, each enrolled patient will taper dosing of study drug to zero.

The second period is a follow-up observation period of 40 weeks, including the tapering phase and containing 4 interim visits and an end-of-study (EOS) visit. Patients are not to self-administer study drug after approximately Week 14. Patients will be considered to have completed the study with the completion of their EOS visit (scheduled for Week 52).

There are 3 treatment groups: K-321 ophthalmic solution 0.4% dosed 4 times daily (QID); K-321 ophthalmic solution 0.4% dosed 2 twice daily (BID); and placebo.

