Endpoints based on the number and percentage of patients achieving the endpoint (patients who achieve central ECD of 700 cells/mm² or more, patients who achieve cornea clearance at each visit, patients who achieve a cornea thickness less than or equal to baseline cornea thickness at each visit, and patients who have no corneal oedema at each visit) will be analysed by pairwise Fisher's Exact or Pearson chi-square tests comparing each active K-321 0.4% treatment regimen to placebo. The 95% CI for the difference in percentage of patients achieving the endpoint will also be presented.

Endpoints based on time-to-event endpoints (time to achieve central ECD 700 cells/mm² or more, time to cornea clearance, time to return of cornea thickness to less than or equal to baseline cornea thickness, time to no corneal oedema) will be analysed by pairwise

log-rank tests comparing each active K-321 0.4% treatment regimen to placebo. Kaplan-Meier estimates and plots will also be presented. Patients who complete follow-up or discontinue the study without achieving the specified endpoint will be [REDACTED]. Patients who receive rescue keratoplasty will be [REDACTED].

Safety parameters include monitoring of AEs, TEAEs, vital sign measurements, laboratory examinations, slit-lamp biomicroscopy, IOP, and ophthalmoscopy. Safety data will be summarised and listed with no statistical hypothesis testing performed.

Continuous variables will be summarised using the mean, the SD, median, minimum value, and maximum value. Categorical variables will be summarised using frequency counts and percentages.

Version and Date of Protocol:

Version 2.0, 31 December 2019

List of Abbreviations

Abbreviation	Definition
AE	adverse event
BCVA	best controlled visual acuity
BID	twice daily
CFR	Code of Federal Regulations
CI	confidence interval
CRO	contract research organisation
CS	clinically significant
CV	curriculum vitae
DMEK	Descemet membrane endothelial keratoplasty
DSEK	Descemet stripping endothelial keratoplasty
DSO	Descemet stripping only
ECD	endothelial cell density
eCRF	electronic case report form
EDC	electronic data capture
EOS	end-of-study
EOT	end-of-treatment
ETDRS	Early Treatment Diabetic Retinopathy Study
FAS	full-analysis set
FDA	US Food and Drug Administration
FECD	Fuchs endothelial corneal dystrophy
GCP	Good Clinical Practice
HbA1c	haemoglobin A1c (glycated haemoglobin)
HRT	Heidelberg retina tomography
ICF	informed consent form
ICH	International Council for Harmonisation

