5.8.3.2 Prohibited and Restricted Medication

The following medications and drugs identified as exclusion criteria are prohibited for use by patients throughout the study:

- Netarsudil or other ROCK inhibitors
- Eye drops and ointments containing 5% sodium chloride
- Devices to improve any ocular symptoms (eg, TrueTear®, LipiFlow®, etc)
- Drugs of abuse (opiates, methadone, cocaine, amphetamines, barbiturates, or benzodiazepines) or more than 2 standard drinks of alcohol per day. Subjects in countries which have lower thresholds for alcohol intake must follow their country's own recommendations and limits for alcohol consumption.
- Contact lenses (except non-study eye)

- Any ophthalmic solution besides artificial tears, over-the-counter anti-allergic ophthalmic products, study drug, or drugs prescribed by the investigator for treatment of the underlying condition
- Any investigational drug besides study drug

6 Study Assessments and Procedures

Before performing any study procedures, all potential patients will sign an informed consent form (ICF). Patients will have the opportunity to have any questions answered before signing the ICF. The investigator must address all questions raised by the patient. The investigator or designee will also sign the ICF.

The SOA is presented in [Table 6-1](#). Detailed instructions for study site activities will be provided in the study manual.

Table 6-1 Schedule of Study Site Activities

Activity	Screening	Treatment Period										Follow-Up Period				
	Time Point	Day -28	Day -1	Day 1	Week 1	Week2	Week 3	Week 5	Week 7	Week 9	Week 12	Week 16	Week 20	Week 24	Week 38	Week 52
Visit Window (Day)	-28 to -7	-	-	5-9	12-16	18-24	32-38	46-52	60-66	81-87	105-119	133-147	161-175	259-273	357-371	
Visit No.	Visit 1	Visit 2	Visit 3	Visit 4	Optional Visit	Visit 5	Visit 6	Visit 7	Visit 8	Visit 9	Visit 10	Visit 11	Visit 12	Visit 13	Visit 14	
Informed consent	X															
Demographics	X															
Medical history and concomitant disease	X	X ^a														
Physical examination and vital sign measurements	X									X						
Urine drug screen	X															
Urine pregnancy test (if applicable)		X ^a									X					
Laboratory sampling	X									X						
Eligibility evaluation	X	X ^b														
Descemetorhexis with photo or video documentation		X														
Randomisation		X														
Dispense study drug			X	X		X	X	X	X	X						
study drug ^c				X	(X) ^d	X	X	X	X	X	X					
Study drug administration			X	X	(X) ^d	X	X	X	X	X						

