Slit-lamp evaluation	X	X ^a	X	X	(X) ^d	X	X	X	X	X	X	X	X	X	X	
Corneal ECD measurement ^e (specular microscopy, non-contact type)	X			X	(X) ^d	X	X	X	X	X	X	X	X	X	X	
Corneal ECD measurement by HRT ^f	(X)			(X)	(X) ^d	(X)	(X)	(X)	(X)	(X)	(X)	(X)	(X)	(X)	(X)	

Activity	Screening	Treatment Period										Follow-Up Period				
	Time Point	Day -28	Day -1	Day 1	Week 1	Week2	Week 3	Week 5	Week 7	Week 9	Week 12	Week 16	Week 20	Week 24	Week 38	Week 52
Visit Window (Day)	-28 to -7	-	-	5-9	12-16	18-24	32-38	46-52	60-66	81-87	105-119	133-147	161-175	259-273	357-371	
Visit No.	Visit 1	Visit 2	Visit 3	Visit 4	Optional Visit	Visit 5	Visit 6	Visit 7	Visit 8	Visit 9	Visit 10	Visit 11	Visit 12	Visit 13	Visit 14	
BCVA (ETDRS scale)	X			X	(X) ^d	X	X	X	X	X	X	X	X	X	X	
Corneal thickness (ultrasound pachymeters)	X			X	(X) ^d	X	X	X	X	X	X	X	X	X	X	
Corneal morphology (Pentacam or Orbscan)	X			X	(X) ^d	X	X	X	X	X	X	X	X	X	X	
Contrast sensitivity ^f (CSV-1000 chart)	X			X	(X) ^d	X	X	X	X	X	X	X	X	X	X	
Intra-ocular pressure (contact or non-contact type tonometer)	X		(X) ^g	X	(X) ^d	X	X	X	X	X	X	X	X	X	X	
██████	X						X			X			X		X	
Photo documentation of ocular findings	X			X	(X) ^d	X	X	X	X	X	X	X	X	X	X	
Concomitant therapy	X	X	X	X	(X) ^d	X	X	X	X	X	X	X	X	X	X	
Adverse event documentation		X	X	X	(X) ^d	X	X	X	X	X	X	X	X	X	X	

Abbreviation: HRT, Heidelberg retina tomography; ██████████ ██████████

- ^a Pre-operative.
- ^b Post-operative.
- ^c Both ██████████ study drug ██████████ will ██████████ and ██████████ will be recorded in the eCRF. Morning/night and mid-day/evening drug will ██████████ separately. At the optional Week 2 visit, a patient's study drug will ██████████ returned to the patient. At Visit 10, study drug ██████████ from the drug tapering phase (Week 12 through Week 14) will ██████████.
- ^d Week 2 is an optional visit (at the discretion of the investigator), but if this visit is applied, all marked assessment items must be conducted.
- ^e The study eye must be measured at all indicated visits, whereas the non-study eye must be measured only at Visit 1 and Visit 14.
- ^f Only at sites where equipment is available.
- ^g If investigator judges it necessary.

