7.2 Secondary Efficacy Endpoints

Secondary efficacy endpoints include:

- Central corneal thickness change from baseline to each subsequent visit
- Percent change of central corneal thickness from baseline to each subsequent visit
- Central corneal ECD at each visit
- Number and percentage of patients who achieve central corneal ECD of 700 cells/mm² or more at each visit
- Time to achieve central corneal ECD 700 cells/mm² or more
- Number and percentage of patients who achieve cornea clearance at each visit where corneal clearance is defined as patients achieving a cornea thickness less than or equal to baseline cornea thickness and who have no corneal oedema
 - Number and percentage of patients who achieve cornea thickness less than or equal to baseline cornea thickness
 - Number and percentage of patients who achieve no corneal oedema
- Time to cornea clearance

- Time to return of cornea thickness to less than or equal to baseline cornea thickness
- Time to no corneal oedema

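### Healing times are seen only at visits 1 to 14 weeks apart, but only log-rank and Kaplan-Meier are planned; if events are dated at the visit, medians run late and the gain in median tends to be overstated

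*Protocol*

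**What the plan says.** Protocol Section 7.2 lists four time-to-event endpoints among the secondary endpoints: "Time to achieve central corneal ECD 700 cells/mm² or more", "Time to cornea clearance", time to return of thickness to baseline or below, and time to no oedema. The Synopsis (Statistical Methods) and Section 7.7.2 give the same method for all four: "log-rank tests comparing each active K-321 0.4% treatment regimen to placebo. Kaplan-Meier estimates and plots will also be presented".

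The components are measured on the visit schedule in Table 6-1. Its windows, in days, are "5-9 12-16 18-24 32-38 46-52 60-66" for the early visits (the second belongs to the optional Week 2 visit) and "81-87 105-119 133-147 161-175 259-273 357-371" from Week 12 on. The second period is "a follow-up observation period of 40 weeks, including the tapering phase and containing 4 interim visits" before the end-of-study visit.

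Neither the protocol nor the SAP addendum mentions interval censoring or says which date a healing event receives. Section 7.7 leaves data conventions to the SAP. The only SAP supplied is an addendum, which states that it does not repeat the primary SAP v2.0. The one event-time formula it shows (Figure 14.2.1.42) is for rescue therapy, not healing.

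**The concern.** A cornea first found healed at a visit healed at some point since the previous visit. Kaplan-Meier needs a single date, and the visit is the only one that the schedule supplies. Dating the event there adds on average about half a gap: roughly 1 week up to Week 9, 1.5 weeks between Weeks 9 and 12, 2 weeks between Weeks 12 and 24, and 7 weeks after Week 24. Giving all arms the same schedule does not cancel this, because the slower arm heals later, where gaps are wider. A missed visit adds a further gap.

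The Introduction gives the medical need as a drug that speeds healing. Readers will therefore look at the median times and their difference, and part of that difference could reflect the visit calendar.

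**Working it through.** **Schedule.** The documents give no median, event count or power for these endpoints, so there is no planned figure to reproduce. The visit grid can be checked. Midpoint of each Table 6-1 window divided by 7: 7/7 = 1, 21/7 = 3, 35/7 = 5, 49/7 = 7, 63/7 = 9, 84/7 = 12, 112/7 = 16, 140/7 = 20, 168/7 = 24, 266/7 = 38, 364/7 = 52. The gaps are 1, 2, 2, 2, 2, 3, 4, 4, 4, 14 and 14 weeks. The optional Week 2 visit is left out.

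**Direction in one comparison.** With visit dating, the large-sample Kaplan-Meier median is the first visit at or after the true median.
- True 5 v 10 weeks becomes 5 v 12: gain 5 becomes 7.
- True 5.2 v 8.8 becomes 7 v 9: gain 3.6 becomes 2.
- True 12 v 18 becomes 12 v 20: gain 6 becomes 8.

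Over all pairs with the drug median below the placebo median, and both within Weeks 1 to 12, the mean bias is +0.04 week (45% overstated, 52% understated). Within Weeks 1 to 24 it is +0.32 week (54% over, 43% under).

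**Average size at the planned sample size.** Assumptions that are not in the documents: log-normal healing times with log SD 0.6, no missed visits, no rescue surgery. The 20 patients per arm come from Section 7.4. There were 20,000 simulated trials per setting. Non-healers count in an arm's median: if a share c ever heals, the arm median is the healers' quantile at 0.5/c. At c = 0.85 that is the 0.588 quantile (z = 0.223), so arm median = healer median × exp(0.6 × 0.223) = 1.143 × healer median; for example 8 × 1.143 = 9.1 weeks. At c = 0.66 the factor is 1.52. The 66% follows the Introduction's 31 of 47 untreated cases that cleared (31/47 = 66.0%, printed there as 65%).

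| True arm medians (weeks) | Ever healing | Reference gain | Visit-dated gain | Excess | Interval-based gain |
|---|---|---|---|---|---|
| 4 v 6 | 85% | 1.96 | 1.92 | −0.04 | – |
| 5 v 8 | 85% | 2.95 | 3.17 | +0.22 | – |
| 6 v 9 | 85% | 2.96 | 3.28 | +0.32 | – |
| 8 v 12 | 85% | 3.93 | 4.56 | +0.63 | – |
| 9.1 v 13.7 | 85% | 4.6 | 5.1 | +0.5 | 4.7 |
| 12.2 v 18.2 | 66% | 6.1 | 7.0 | +0.9 | – |
| 9.1 v 18.2 | 85% v 66% | 9.1 | 10.7 | +1.6 | 10.3 |
| 12.2 v 24.3 | 66% | 12.2 | 14.4 | +2.2 | – |
| 11.4 v 22.9 | 85% | 11.4 | 14.1 | +2.7 | 11.9 |
| 13.7 v 27.4 | 85% | 13.7 | 18.2 | +4.5 | 14.5 |

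In the first four rows the reference is the mean gain with exact times; below them it is the true difference, computed before rounding the medians. Interval-based means the median interpolated within its visit interval.

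**Other shapes.** With exponential times and hazard ratios of 1.5 to 2, the excess is 0.03 to 0.2 week at placebo medians of 6 to 8 weeks, 0.5 to 0.7 at 12, 0.8 to 1.1 at 16, and 2.7 to 3.5 at 26. With 35% never healing (Weibull, shape 1.5) and hazard ratio 2, it is 0.4 to 1.5 weeks.

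**Log-rank test.** At hazard ratio 1 the rejection rate is 0.050 to 0.059 visit-dated and 0.050 to 0.060 with exact times. In the exponential model at hazard ratio 2, power is 0.506 to 0.556 against 0.512 to 0.571. The largest loss in any one setting is 0.564 − 0.540 = 0.024.

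**The case against.** A reader might infer that the drug's gain will be overstated, perhaps by a quarter or a third: 14.1/11.4 is about +23% and 18.2/13.7 about +33%. The documents do not support that. Those settings need a slow-arm median of 22.9 or 27.4 weeks, whereas the Introduction says that oedema persisting at 6 months was unlikely to resolve. Under the same model, 33% and 45% of all healing in that arm would come after Week 26, and 65% and 72% of eyes unhealed at Week 26 would still heal. This objection stands for oedema and clearance. It is weaker for time to a cell density of 700 or more, on which the Introduction gives no time limit.

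In the earlier settings the bias is small beside sampling error. The SD of the gain is 1.5 to 3.1 weeks in the first four rows of the table and 3.4 weeks at 9.1 v 13.7. Visit dating gave the smaller gain in 52% of trials at 4 v 6 weeks and in 36% at 9.1 v 13.7. Overstatement is therefore an average tendency and cannot be predicted for this trial.

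A reader might also infer that the log-rank comparison is invalid. It is not, because all arms share one schedule. Replacing it would be a preference.

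Finally, the dating rule may be set out in primary SAP v2.0, and the handling of censoring and rescue is redacted. The simulations ignore rescue keratoplasty, which may be offered from Week 12, or earlier if urgent. By-visit proportions for the same states are planned as well and have no dating problem. All of this stands. It limits the size and certainty of the point, but the supplied plan still pairs visit-only observation with Kaplan-Meier summaries alone.

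**Conclusion.** The four healing-time endpoints are interval-censored, and the supplied plan summarises them only by Kaplan-Meier. If events are dated at the visit, which is likely but not stated, each median is late and the gain in median is on average too large. Under the assumed log-normal times, the excess is near zero for medians of about 4 to 6 weeks and roughly 0.5 to 1 week for medians of about 8 to 18 weeks. It was 1.6 weeks in the one setting where the arms also differ in the share that heals. It reaches several weeks only when the slower arm's median is near or beyond Week 24, which the protocol's own evidence makes unlikely for oedema. Every size here depends on assumed healing distributions, and an individual comparison can go the other way.

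The log-rank test holds its size and loses at most 2 to 3 points of power. These are secondary endpoints without multiplicity control (Section 7.7), and the primary analysis is untouched. The change is a cheap improvement and corrects no error in the trial's main inference.

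**What to change.** - State the event-date rule for the four endpoints, including how the optional Week 2 visit, unscheduled visits and missed visits are used. Extra visits that differ by arm would break the common-schedule argument for the log-rank test.
- Define each patient's interval from the last visit without the event to the first visit with it, right-censored at the last visit without it.
- Report quartiles from the non-parametric interval-censored (Turnbull) estimate, or as visit intervals.
- Keep the log-rank test. A generalised log-rank test is optional.
- Keep the Kaplan-Meier curves, labelled 'time to first visit at which the event was recorded'.

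The cost is some SAP wording and one extra analysis of existing data. Quartiles will look less sharp because they lie within visit intervals. Interval estimation reduces the bias without always removing it: at 9.1 v 18.2 weeks with unequal healing shares it gives 10.3, against 10.7 by Kaplan-Meier and a true 9.1.

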2.1 Primary Objective

The primary objective of this study is to investigate the effect of K-321 dosed for 12 weeks on central ECD in patients with FECD after descemetorhexis.

2.2 Secondary Objectives

The secondary objectives of this study are the following:

- to investigate the effect of K-321 on central ECD, corneal thickness, and corneal clarity in patients with FECD at each visit after descemetorhexis out to 52 weeks
- to assess the safety and tolerability of K-321 in patients with FECD at each visit after descemetorhexis out to 52 weeks

2.3 Exploratory Objectives

[REDACTED]

[figure not shown]
3 Investigational Plan

3.1 Study Design

This is a multi-centre, double-masked, randomised, parallel-group, placebo-controlled, 2-period study of patients with FECD after descemetorhexis. The study design is presented in [Figure 3-1](#), and the schedule of study site activities (SOA) is presented in [Table 6-1](#).

The first period is the treatment period, consisting of a screening visit within a 1- to 4-week screening period, a descemetorhexis and randomisation visit, a 12-week full treatment period containing 7 interim visits (including 1 optional visit at Week 2) and an end-of-treatment (EOT) visit scheduled for Week 12. During the 2 weeks immediately following the EOT visit, each enrolled patient will taper dosing of study drug to zero (Section [5.2](#)).

The second period is a follow-up observation period of 40 weeks, including the tapering phase and containing 4 interim visits and an end-of-study (EOS) visit. Patients are not to self-administer study drug after approximately Week 14. The maximum total study period for each enrolled patient is 56 weeks, with a maximum of 15 visits (including the 1 optional visit). Patients will be considered to have completed the study with the completion of their EOS visit (scheduled for Week 52). The duration of the study is defined for each patient as the date signed written informed consent is provided through the last follow-up visit.

There are 3 treatment groups: K-321 ophthalmic solution 0.4% dosed QID, K-321 ophthalmic solution 0.4% dosed BID, and placebo. The procedures for randomly assigning study drug are presented in Section 5.1.

After obtaining informed consent at Visit 1, the investigator will select one eye as the study eye, and the patient will come back for the descemetorhexis operation and random assignment to treatment after 1 to 4 weeks (Visit 2). At Visit 2, each patient's eligibility for study participation will be confirmed, including a successful descemetorhexis operation that meets the inclusion criteria (Section 4.1). Guidance for the descemetorhexis will be provided in the study manual. Recommended post-descemetorhexis concomitant therapy is described in Section 5.8.1. Documentation of the descemetorhexis is discussed in Section 6.1.

After eligibility is confirmed, patients will be randomly assigned to the 3 treatment groups (in a 1:1:1 ratio). All patients will be instructed to apply the study drug only to the study eye.

Except on days of study visits on Day 1 through Week 12 (not including Visit 9) during the treatment period, study drug will be dosed by the patient QID (Section 5.2): morning (9 AM \pm 1 hour), mid-day (1 PM \pm 1 hour), evening (5 PM \pm 1 hour), and night (9 PM \pm 1 hour). Each patient will be provided with 2 sets of colour-coded [REDACTED], one set to be applied

morning and night (M/N) and the other to be applied mid-day and evening (MD/E). See Section 5.4.1 for a detailed description of packaging.

On study visit days Visit 3 through Visit 9, patients will not apply any study drug until after all study measurements have been completed; thereafter on those days, patients will start dosing with the dose closest in timing to the dosing regimen and continue with the remaining doses for the day. Additionally, on Visit 3 they must first apply the study drug within [REDACTED] after the end of the descemetorhexis procedure on Day –1 (Visit 2).

With the primary efficacy endpoint being assessed at Visit 9 (Week 12), if a patient applies any study drug on the day of Visit 9 before all study measurements have been completed, that patient's Visit 9 should be rescheduled within the visit window allowance (eg, the next day). For visits other than Visit 9 during the treatment period, a patient who applies study drug before all study measurements have been completed will be assessed as planned, and a protocol deviation must be recorded.

At Visit 9 (Week 12), patients will enter the drug-tapering phase of the follow-up period, and new study drug will be dispensed without M/N or MD/E colour coding (Section 5.2). All patients will self-administer their tapering-phase study drug BID (9 AM \pm 1 h and 9 PM \pm 1 h) for a week, then once daily (9 AM \pm 1 h) for a week, and then will discontinue study drug. At Visit 9, patients will apply the first dose of study drug [REDACTED] of completing study measurements and will apply the second dose at night, as scheduled.

During the follow-up period, patients will attend 5 study visits (Figure 3-1), starting at Week 16 (Visit 10).

Study activities and assessments will be performed at study visits as described in Table 6-1 and in Section 6. [REDACTED] will determine central ECD by analysing digital images of the corneal endothelium (Table 11-1).

Keratoplasty may be offered as a rescue surgical procedure to an enrolled patient if the investigator judges that endothelial healing is not complete at Visit 9 (Week 12), or earlier if the investigator considers that the patient needs urgent treatment (Section 5.8.2).

4 Patient Selection and Discontinuation/Withdrawal Criteria

